8.7.1.4 Analysis of Exploratory Efficacy Endpoint

If there exists exploratory efficacy endpoints analysis, it will be included in separate analysis documents.

8.8 Safety Analyses

8.8.1.1 Adverse Events

AEs will be coded according to MedDRA (version 23 or higher). The severity of adverse events will be judged in accordance with NCI CTCAE 5.0. The number and percentage of subjects experiencing an AE will be summarized by System Organ Class and Preferred Term. AEs will be classified as pretreatment or treatment-emergent.

Treatment-emergent AEs (TEAEs) are defined as AEs that were reported or worsened on or after the start of study drug dosing and up to the safety follow-up.

For any SAE that occurs after the safety follow-up and was related to study drug, it will be considered to a TEAE.

Missing or partial dates will be imputed for AE. Algorithm for missing or partial start date is:

Missing day: if month/year equal to month and year of first dose date, then impute to date of the first dose; else impute to first day of the month.

Missing month: if year equal to year of first dose date, then impute to date of the first dose; else impute to Jan01 of the year.

Missing year: impute to first dose date if first dose date < AE end date, else impute to ICF date.

Algorithm for missing or partial end date is:

Missing day: last day of the month is imputed;

Missing month: impute to 31 December

Missing year: not imputed.

Missing data algorithms will be reviewed to ensure the algorithm works. For example, end date will not be before the start date after the imputation.

Only TEAEs will be summarized in tables.

The overall TEAE summary will include the following:

All TEAEs (regardless of relationship to study drug)

Grade \geq 3 TEAEs

Treatment related TEAEs

Treatment related Grade \geq 3 TEAEs

Serious TEAEs

Treatment related serious TEAEs

TEAEs leading to dose reduced

TEAEs leading to dose interrupted
TEAEs leading to study drug withdrawn
TEAEs leading to Death
Treatment related TEAEs leading to dose reduced
Treatment related TEAEs leading to dose interrupted
Treatment related TEAEs leading to study drug withdrawn
Treatment related TEAEs leading to Death

The TEAEs, TEAEs related to study drug, TEAEs leading to study drug withdrawn, Treatment related TEAEs leading to study drug withdrawn, Grade ≥ 3 TEAE, Treatment related Grade ≥ 3 TEAEs, TEAE by worst CTCAE Grade, Treatment related TEAEs by worst CTCAE Grade, Serious TEAEs, Treatment related serious TEAEs, TEAE leading to dose reduced, Treatment related TEAEs leading to dose reduced, TEAE leading to dose interrupted, Treatment related TEAEs leading to dose interrupted, TEAEs leading to death, Treatment related TEAEs leading to death, TEAEs with an Incidence Rate $\geq 10\%$ and Treatment related TEAEs with an Incidence Rate $\geq 10\%$ summary will be presented by MedDRA system organ class and preferred term using frequency counts and percentages in descending order of frequency separately.

The number and percentage of subjects with death and the primary cause will be summarized and listed for subjects in the Safety Analysis Set.

All AEs, Serious AEs and AEs leading to Death will be listed in an individual subject data listing.

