10.6.7 Handling of missing values/censoring/discontinuations

10.6.7.1 Date Values

In cases of incomplete dates (e.g., pertaining to AE, concomitant medication, medical history, etc.), the missing component(s) will be assumed as the most conservative value(s) possible. For example, if the start date has a missing day value, the first day of the month will be imputed for study day computations (i.e., treatment-emergent status, etc.). If day is missing for an end date, the last day of the month will be imputed. Similar logic will be assumed for missing month and year components.

Date imputation will only be used for computational purposes e.g., treatment-emergent status, etc. Actual data values as they appear in the original CRFs will be shown in the data listings.

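### Applied literally, the SAP's missing-start-year rule classes an ongoing AE, or one ending on the day of first dose, as pretreatment

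*SAP*

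**What the plan says.** SAP 8.8.1.1 divides events into two classes: "AEs will be classified as pretreatment or treatment-emergent". The definition (cut short here; its window closes at the safety follow-up) reads "Treatment-emergent AEs (TEAEs) are defined as AEs that were reported or worsened on or after the start of study drug dosing and up to the". The tables are restricted to one class: "Only TEAEs will be summarized in tables".

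For a start date with no year, the rule is "Missing year: impute to first dose date if first dose date < AE end date, else impute to ICF date". For an end date with no year, the same section says "Missing year: not imputed".

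Protocol 10.6.7.1 sets the principle for incomplete dates, that "the missing component(s) will be assumed as the most conservative value(s) possible", and ties it to classification: "Date imputation will only be used for computational purposes e.g., treatment-emergent status, etc". SAP 8.1 likewise asks for conservative conventions where partial dates are imputed. The list of departures from the protocol in SAP 8.12 does not mention this rule.

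**The concern.** The rule needs an end date later than first dose before it will place the start at first dose. Every other case goes to consent. An event that is still continuing has no end date, so it cannot meet the condition, although it is the event most clearly present during treatment. An event that ended on the day of first dose fails too, because the inequality is strict.

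AE incidence is part of the Phase I primary endpoint (Protocol Section 3; SAP 4.1), and the tables show TEAEs only. For ongoing events the rule can only lower the tabulated incidence, and the events it removes are unresolved ones.

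**Working it through.** The plan gives no figure to reproduce. The check is to run the rule through the possible end dates.

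**Inputs**
- Rule: if first dose < AE end date, start = first dose; otherwise start = consent date (SAP 8.8.1.1).
- An end date with no year stays missing (SAP 8.8.1.1).
- Consent falls before first dose: it precedes all study procedures (Protocol 5.2, criterion 1), and screening runs from Day -28 to Day -1 (Protocol Table 7-1).
- Assumption: a comparison with a missing end date counts as not satisfied. SAP 8.1 names SAS 9.4, where a missing number sorts below any number, so the comparison is false. That is general software behaviour and is not stated in the documents.

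**Cases, start year missing, event not recorded as worsening**

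| AE end date | first dose < end date? | Start as written | Class as written | Class under the fix |
|---|---|---|---|---|
| Day before first dose | No | Consent | Pretreatment | Pretreatment |
| Day of first dose | No | Consent | Pretreatment | TEAE |
| Day after first dose | Yes | First dose | TEAE | TEAE |
| None (ongoing, or year missing) | Not satisfied | Consent | Pretreatment | TEAE |

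The result is the same with consent at Day -28 or at Day -1. An event that resolved one day after dosing is counted, and one that never resolved is not. If the programmer instead treats an ongoing event as ending after any date, the last row becomes a TEAE as written, but the second row does not change.

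**Comparison with medications.** SAP 8.5 counts a medication as concomitant if it stopped on or after first dose, or if its stop date is missing. The two end-date patterns that make a medication on-treatment therefore make an adverse event pretreatment when its start year is missing.

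**Size, as an illustration.** Protocol 1.2.1.2 gives escalation cohorts of 3 (25 and 50 mg BID) and 4 (100 mg BID; 400, 600 and 800 mg QD) at the January 2022 cutoff, plus 4 expansion patients at 600 mg QD. If one patient's only occurrence of a term is lost:
- cohort of 3: 1/3 = 33 percentage points;
- cohort of 4: 1/4 = 25 points;
- 600 mg QD with escalation and expansion pooled: 1/(4 + 4) = 12.5 points;
- patient has another TEAE with the same term: 0 points.

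**The case against.** The strongest reply is that the SAP never says ongoing events go to consent. Ongoing is a recorded status (Protocol 8.1.3 has a not-resolved outcome), and a programmer guided by the conservative principle could treat it as an end date after first dose. That is a fair reading of intent. But the text is an explicit either/or whose second branch takes everything that fails the first, and it gives no instruction for ongoing events. Nor does this reading rescue the event ending on the day of first dose.

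Four stronger readings are tempting, and the documents do not support them:
- *Every such event vanishes from every TEAE table.* The definition also admits events that worsened after dosing, so an ongoing event recorded as worsening still counts.
- *The rule reverses the SAP's other start-date rules.* The missing-day and missing-month rules use first dose only when the known part of the date matches it; otherwise they use the first of the month or 1 January. They are not a general default to first dose.
- *The MTD or RP2D is at risk.* Escalation uses DLTs directly (Protocol 6.2.3 and 6.2.4), and DLTs have their own listing (SAP 8.8.1.2).
- *The events disappear from the report.* The SAP says "All AEs, Serious AEs and AEs leading to Death will be listed in an individual subject data listing", and Protocol 10.6.7.1 keeps the original dates in listings. Deaths are also summarised separately.

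It is also fair that the case should be rare. Events are sought at each visit from consent onward (Protocol 8.1.2), start and end dates are to be determined (8.1.3), missing values are queried (9.5), and the study stopped early with fewer patients than planned (SAP Section 7).

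The SAP's general promise to review its missing-data algorithms is a partial safeguard. Its only example is an end date falling before the start date, and an ongoing event placed at consent raises no such conflict.

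Finally, the word for reporting in the TEAE definition could be read as the date of report, which would make the imputed start irrelevant. Protocol 10.6.7.1 points the other way, since it names treatment-emergent status as a use of imputed dates.

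**Conclusion.** The point holds as a minor defect in a stated rule. Read literally, the rule gives the less conservative class to ongoing events and to events ending on the day of first dose when the start year is missing. This departs from Protocol 10.6.7.1 and SAP 8.1 and is inconsistent with SAP 8.5. The loss is confined to the TEAE tables and to events not recorded as worsening.

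No expected size can be given, because the documents do not say how many start years are missing. The 25 to 33 points are an upper bound for one lost event in a cohort of 4 or 3. Any single event would do the same in cohorts that small, so the figure is not evidence that the rule will bite. For ongoing events, the conclusion assumes that a missing end date is handled as failing the comparison.

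**What to change.** Replace the missing-year sentence for AE start dates in SAP 8.8.1.1 with wording such as:

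*Year missing: set the start to the date of first dose, unless the recorded end date (after any partial-date imputation) is before first dose; in that case set it to the date of consent. If the event is ongoing or has no end date, set the start to the date of first dose.*

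This covers the ongoing case, the same-day case and the order in which the end date is imputed. It costs one sentence and about one line of code. The downside is that a few events that truly began before treatment may be counted as TEAEs, which is the direction the protocol's conservative principle accepts.

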8.8.1.2 Dose Limiting Toxicity (DLT)

The listing for dose limiting toxicity will be provided.

8.8.1.3 Laboratory Test Results

Hematology, blood biochemistry and urinalysis will be conducted in the screening period, treatment period and follow-up period according to study process, and examination frequency will be increased according to clinical indications.

Specific evaluation items include:

- Hematological test: red blood cell count, hemoglobin, hematocrit, reticulocyte count, platelet count and absolute leukocyte differential count (neutrophil, lymphocyte, eosinophils, monocyte, basophils);
- Blood biochemical test: Total protein, albumin, total bilirubin, direct bilirubin, ALT, AST, Gamma-glutamyl transferase, Creatine phosphokinase, Alkaline phosphatase, Lactate dehydrogenase, Blood urea nitrogen, Urea, Creatinine, Uric acid, Blood glucose, Chloride, Sodium, Potassium, Calcium, Phosphate, Amylase, Lipase and CKMB.
- Urinalysis: specific gravity, urine glucose, protein, white blood cell (qualitative) and red blood cell (qualitative);

- Coagulation function test: prothrombin time, activated partial thromboplastin time and international normalized ratio;

- Pregnancy test (applicable to non-menopausal women);

An observed value and change from baseline in laboratory by visit descriptive table will be provided by treatment group.

For serum chemistry, hematology and urinalysis data, a shift table between the worst post-baseline clinical significance and baseline clinical significance will be provided by treatment group.

For liver safety, summaries of the liver chemistry elevations will be presented in the table according to Table .

Table 1 Liver Chemistry Elevations

Test	Category
ALT or AST increased	$\geq 3 * \text{ULN}$
	$\geq 5 * \text{ULN}$
	$\geq 10 * \text{ULN}$
	$\geq 20 * \text{ULN}$
ALT increased	$\geq 3 * \text{ULN}$
	$\geq 5 * \text{ULN}$
	$\geq 10 * \text{ULN}$
	$\geq 20 * \text{ULN}$
AST increased	$\geq 3 * \text{ULN}$
	$\geq 5 * \text{ULN}$
	$\geq 10 * \text{ULN}$
	$\geq 20 * \text{ULN}$
TBIL increased	$\geq 1.5 * \text{ULN}$
	$\geq 2 * \text{ULN}$
ALP increased	$\geq 1.5 * \text{ULN}$

In additional, ALT or AST $\geq 3 * \text{ULN}$ and TBIL $\geq 2 * \text{ULN}$ and ALP $< 2 * \text{ULN}$, ALT or AST $\geq 3 * \text{ULN}$ and TBIL $\geq 2 * \text{ULN}$, ALT and AST $\geq 3 * \text{ULN}$ and TBIL $\geq 1.5 * \text{ULN}$ will also presented in this table.

The listing for abnormal findings in laboratory data will be provided.

8.8.1.4 Vital Signs

An observed value and change from baseline in vital sign by visit descriptive table will be provided by dose group.

The number and percentage of subjects with abnormal changes (defined in [Appendix D](#)) in systolic blood pressure, diastolic blood pressure, pulse/heart rate, respiratory rate and

temperature will be summarized for subjects in the safety analysis set. A shift table between the worst post-baseline notable abnormalities and baseline notable abnormalities will be provided by treatment group.

A vital sign data listing will be provided.

8.8.1.5 Physical Examination

General physical examination: including General appearance, Skin, Neck, Eyes, Ears, Nose, Throat, Lungs, Heart, Abdomen, Back, Lymph nodes, Extremities, Vascular, Neurological and other.

For each general physical examination, a shift table between the worst post-baseline clinical significance and baseline clinical significance will be provided by dose group.

The listing for abnormal PE findings will be provided. The listing for abnormal ophthalmological examinations will be provided in another listing.

8.8.1.6 Analysis of 12-lead ECG

12-lead ECG: Including heart rate, PR interval, QRS interval, QT interval, QTcF interval and diagnosis.

An observed value and change from baseline in ECG by visit descriptive table will be provided by dose group.

A shift in Clinical Evaluation table from baseline to worst post-baseline value will be presented.

A 12-lead ECG listing will be provided for all subjects in the Safety analysis Set.

8.8.1.7 Analysis of ECOG

A shift table between the worst post-baseline ECOG Performance Status and baseline ECOG Performance Status will be provided by dose group.

8.9 Pharmacokinetic Analysis

Pharmacokinetic parameters will be determined with non-compartmental analysis method with PK Analysis Set.

Samples for PK analysis of HH2710 and selected metabolites will be obtained from all Phase I/II patients during their first cycle of treatment (Cycle 1). PK samples will also be obtained from additional patients in Phase II depending on the outcome of initial PK analysis.

Below is the list of various PK parameters that will be calculated after Dose 1 (Day 1) and at Steady State (Day 22).

Table 2 PK parameters Description

PK Parameter (plasma)	Description
C_{\max}	Peak plasma concentration determined manually by visual inspection of plasma concentration vs. time figures on the untransformed (linear) scale of measurement

t_{max}	Time to reach the peak plasma concentration determined manually by visual inspection of plasma concentration vs. time figures on the untransformed (linear) scale of measurement
AUC_{0-12}	Area under the plasma concentration-time curve from 0 to 12 hours postdose, calculated by linear/log trapezoidal method
AUC_{0-last}	Area under the plasma concentration-time curve from time 0 to time of last observation after dosing calculated by linear/log trapezoidal method
Lambda_z (λ_z)	Terminal phase rate constant, determined by linear regression of at least 3 points on the terminal phase of the log-linear plasma concentration-time curve. The correlation coefficient (r^2) for the goodness of the fit of the regression line through the data points has to be 0.85 or higher for the value to be considered reliable. If the WinNonlin data points are not on the linear portion of the terminal slope, the data points will be selected manually prior to calculation of Lambda_z
$t_{1/2}$	Terminal half-life, defined as $0.693 / \lambda_z$
CL/F	The total body clearance of drug from the plasma (volume x time-1)
V_z/F	The apparent volume of distribution during terminal phase (associated with λ_z)(volume)

Descriptive statistics [n, arithmetic mean, standard deviation, coefficient of variation (CV), median, minimum, maximum, geometric mean, geometric standard deviation geometric CV] will be used to summarize PK parameters by treatment. For $t_{1/2}$ and t_{max} , regular descriptive statistics and 95% confidence intervals about the arithmetic mean will be calculated, for each dose.

A listing of blood PK concentrations and parameters will be provided.

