7.1 Study flow and visit schedule

Table 7-1 list all the assessments and indicates with an “X”, the visits when they are performed. All data obtained from these assessments must be supported in the patient’s source documentation.

Screening evaluation must be performed ≤ 28 days of cycle 1 Day 1 except for the pregnancy test which is to be performed within 3 days prior to the first dose of study treatment. Laboratory and radiological assessments performed as part of standard of care prior to signing informed consent

may be used if performed within the screening time window. The time window for tumor biopsies in the Phase I/II may be longer than 28 days.

During the course of the study visits, test and/or procedures should occur on schedule whenever possible. From C2D8, a visit window of +/- 3 days is allowed (with the exception of 30 days safety follow-up visit, for which a visit window of +7 days is allowed).

There is a +/- 7 days window on, tumor response assessment and chest radiological examination after starting study drug.

In particular, full PK sampling with multiple post-dose time points on Day 1 and Day 15 of cycle 1 and other days should be performed on the specified days. (Please refer to PK sampling schedule [Table 7-7-2](#) and [错误!未找到引用源。7-3](#)). The first three patients should perform single dose full PK sample collecting in the first day.

The assessment type please see [Section 7.2](#).

Unscheduled visit: Additional visits can be performed as appropriate and at the discretion of the investigator

Table 7-1 Visit evaluation Schedule of Assessments and Procedures

Visit name	Protocol Section	Screening period		Study treatment period								follow up period			
		0 molecu lar screeni ng		Cycle 1 Day 1 through 21			Cycle 2 Day 22 through 42			Cycle 3-X 21d/cycle, visit on 1st day of every 2 cycles	End of treatment visit (EOT)/early discontinuation (Section 7.1.4)	Safety follow up	Progress Disease follow up	Survival follow-up (Section 7.1.5.2)	
Visit Day		1 Screening		-28 to -1	1 ± 0	8 ± 1	15 ± 1	22 ± 1	29 ± 3	36 ± 3	43 ± 3	N/A	+ 7	±7	±7
Obtain molecular screening consent (Phase I expansion and Phase II extension)	7.1.1	X													
Informed consent	7.1.2		X												
Inclusion/exclusion criteria	5.2, 5.3		X												
Biomarker detection	7.1.1	X ¹	X												
Medical history/tumor history/tumor treatment history	7.1.2.2		X ²	X	X	X	X	X	X	X	X				
Tumor diagnosis and severity	7.1.2.2		X												

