7.2.2 Pharmacokinetics

7.2.2.1 Blood sample schedule

Study drug will be taken QD at cycle1 day 1 and twice daily from the second day of cycle 1 in the first 3 patients. First dose in clinic on days when PK sampling occurs i.e., Cycle 1 Day 1 and Cycle 1 Day15, remaining doses on all other days to be self-administered by patient.

In order to detect PK of a single administration, for the first 3 patients, a single administration will be given on the first day, administration twice daily from the second day. Patients will undergo serial blood sampling 2ml for PK analysis during cycle 1 on day 1 at pre-dose and 15min, 30min, 1, 2, 3, 4, 6, 8 hours post-dose, and 12 hours post-dose (if available); on day 2 at pre-dose; on cycle1 day 7 (pre-dose), cycle1 day 10 (pre-dose), day 15 at pre-dose and 15min, 30min, 1, 2, 3, 4, 6, and 8 hours post-dose, and 12 hours post dose (if available); and day 16 at pre-dose. On day 22, prior to dose administration, a final blood sample was collected for pharmacokinetic analyses. See [Table 7-2](#), [错误!未找到引用源。3](#).

Serial blood samples will be collected from all patients to assess single dose and multiple dose plasma PK of HH2710 and its metabolite. PK parameters will be derived from each individual plasma concentration-time profiles. Refer to [Section 10.6.4](#) for list of PK parameters that will be estimated.

PK blood sample collection and handling

Blood samples will be taken by either direct venipuncture or an indwelling cannula inserted in a forearm vein. At specified time points described in [Table 7-2](#) and [错误!未找到引用源。3](#), 2 mL blood draws will be collected into tubes containing K2 EDTA and gently inverted several times to thoroughly mix the anticoagulant. Tubes will be centrifuged to separate plasma and plasma will

immediately be transferred into labeled 2 mL polypropylene screw-cap tubes. Plasma samples will be placed in a freezer in an upright position until shipment to the bioanalytical laboratory for analysis.

All sampling is relative to the ingestion of HH2710. On days and time points where blood PD samples are to be drawn, the PK sample must be drawn first. The exact collection date and time of all samples must be documented on the PK blood collection CRF pages. The date and exact time of dosing, as well as the date and actual time of blood sampling must be recorded on the CRF.

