Refer to the [HH2710-G101 Laboratory Manual] for detailed instructions for the collection, handling, and shipment of PK samples.

Intensive PK sampling will be done in the dose escalation portion of the trial. Additional PK sampling will be drawn every two cycles prior to Day 1 dosing in all patients in the dose escalation between Cycle 1 to Cycle 9 (e.g. Cycle 3 Day 1, Cycle 5 Day 1, Cycle 7 Day 1, Cycle 9 Day 1) ([Table 7-2](#)).

PK samples at pre-dose, 2h, 4h, a 6h, 8h, and 24h post dose will also be obtained at Cycle 1 Day 1 and Cycle 1 Day 15 for patients in the Phase I dose expansion stage and Phase II portions of the trial ([Table 7-3](#)).

Table 7-2: PK blood sampling time for Phase I dose escalation stage

CxDx	C1D1	C1D1	C1D1	C1D1	C1D1	C1D1	C1D1	C1D1	C1D1	C1D2	C1D7	C1D10	C1D15	C1D15	
No.	1	2	3	4	5	6	7	8	9	10	11	12	13	14	15
Time	pre-dose	15min	30min	1h	2h	3h	4h	6h	8h	12h (If available)	24h (pre-dose)	pre-dose	pre-dose	pre-dose	15min
Window (min)	-30	±5	±5	±5	±10	±10	±10	±30	±30	±60	-30	-30	-30	-30	±5
Blood Sampling	2mL	2mL	2mL	2mL	2mL	2mL	2mL	2mL	2mL	2mL	2mL	2mL	2mL	2mL	2mL
CxDx	C1D15	C1D15	C1D15	C1D15	C1D15	C1D15	C1D15	C1D15	C1D16	C2D1	C3D1	C5D1	C7D1	C9D1	NA
No.	16	17	18	19	20	21	22	23	24	25	26	27	28	29	NA
Time	30min	1h	2h	3h	4h	6h	8h	12h (If available)	pre-dose	pre-dose	pre-dose	pre-dose	pre-dose	pre-dose	NA
Window(min)	±5	±5	±10	±10	±10	±30	±30	±60	-30	-30	-30	-30	-30	-30	NA

Blood Sampling	2mL	NA											
----------------	-----	-----	-----	-----	-----	-----	-----	-----	-----	-----	-----	-----	----

Table 7-3: PK blood sampling time for Phase I dose expansion stage and Phase II

CxDx	C1D1	C1D1	C1D1	C1D1	C1D1	C1D2	C1D15	C1D15	C1D15	C1D15	C1D15	C1D15
No.	1	2	3	4	5	6	7	8	9	10	11	12
Time	pre-dose	2h	4h	6h	8h	24h	pre-dose	2h	4h	6h	8h	24h
Window(min)	-30	±10	±10	±30	±30	±60	-30	±10	±10	±30	±30	±60
Blood Sampling	2mL	2mL	2mL	2mL	2mL	2mL	2mL	2mL	2mL	2mL	2mL	2mL

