10.6.4 Pharmacokinetic Analysis

Samples for PK analysis of HH2710 and its metabolite will be obtained from all patients enrolled in Phase I dose escalation/expansion and Phase II trial.

Below is the list of PK parameters that will be calculated after single dose (C1D1) and steady State (C1D15).

Table 10-2 PK Parameters Description

PK Parameter (plasma)	Description
C _{max}	Peak plasma concentration determined manually by visual inspection of plasma concentration vs. time figures on the untransformed (linear) scale of measurement
t _{max}	Time to reach the peak plasma concentration determined manually by visual inspection of plasma concentration vs. time figures on the untransformed (linear) scale of measurement
AUC ₀₋₂₄	Area under the plasma concentration-time curve from 0 to 24 hours post-dose, calculated by linear/log trapezoidal method
AUC _{0-∞}	Area under the plasma concentration-time curve from time zero to infinity after dosing calculated by linear/log trapezoidal method
%AUC _{extrap}	Area under the plasma concentration-time curve extrapolated from time t to infinity as a percentage of total AUC (%)
Lambda _z (λ _z)	Terminal phase rate constant, determined by linear regression of at least 3 points on the terminal phase of the log-linear plasma concentration-time curve. The correlation coefficient (r ²) for the goodness of the fit of the regression line through the data points has to be 0.85 or higher for the value to be considered reliable. If the WinNonlin data points are not on the linear portion of the terminal slope, the data points will be selected manually prior to calculation of Lambda _z
t _{1/2}	Terminal half-life, defined as 0.693 (ln2) divided by Lambda z
CL/F	The apparent total body clearance of drug from the plasma (volume x time-1)
V _z /F	The apparent volume of distribution during terminal phase (associated with λ _z)(volume)

Descriptive statistics [n, arithmetic mean, standard deviation, coefficient of variation (CV), median, minimum, maximum, geometric mean, geometric standard deviation geometric CV] will be used

to summarize PK parameters by treatment. For $t_{1/2}$ and t_{max} , regular descriptive statistics and 95% confidence intervals about the arithmetic mean will be calculated, if possible, for each dose. Refer to the PK analysis plan for additional details regarding with the PK analyses.

A listing of blood PK concentrations and parameters will be provided.

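### SAP 8.9 calculates steady-state PK at Day 22, where at most one pre-dose sample is scheduled; the steady-state profile is taken at C1D15

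*SAP*

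**What the plan says.** SAP 8.9 introduces its parameter table with: "Below is the list of various PK parameters that will be calculated after Dose 1 (Day 1) and at Steady State (Day 22". The same section says that PK samples "will be obtained from all Phase I/II patients during their first cycle of treatment (Cycle 1". SAP Table 2 then lists Cmax, tmax, AUC0-12, AUC0-last, lambda-z, half-life, CL/F and Vz/F. Lambda-z is to be "determined by linear regression of at least 3 points on the terminal phase of the log-linear plasma concentration-time curve", and the fixed-interval AUC is "Area under the plasma concentration-time curve from 0 to 12 hours postdose, calculated by linear/log trapezoidal method".

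The protocol differs on the day. Section 10.6.4 reads: "Below is the list of PK parameters that will be calculated after single dose (C1D1) and steady State (C1D15". Section 7.1 requires "full PK sampling with multiple post-dose time points on Day 1 and Day 15 of cycle 1". For Day 22, section 7.2.2.1 says: "On day 22, prior to dose administration, a final blood sample was collected for pharmacokinetic analyses". For the later stages, the same section says that samples "will also be obtained at Cycle 1 Day 1 and Cycle 1 Day 15 for patients in the Phase I dose expansion stage" and for Phase II, with no other day named.

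Protocol Table 10-2 lists AUC0-24, AUC0-inf and %AUCextrap, and none of these is in SAP Table 2. SAP 8.12, which records departures from the protocol, covers matters as small as decimal places and renamed analysis sets, but has no PK entry.

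**The concern.** The SAP's steady-state day is not a day on which a concentration-time profile is collected. Cmax, tmax, AUC0-t, half-life, lambda-z, CL/F and Vz/F are the Phase I secondary endpoints (protocol section 3, SAP 4.1), and both documents plan to report them after a single dose and at steady state. If the SAP is followed literally, the steady-state half of that report is empty although C1D15 samples exist. If the analyst quietly uses C1D15, the report departs from its SAP without a record.

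The AUC substitution adds to this. A 0 to 12 h area fits twice-daily dosing. Since the fourth dose level was opened, much of the dosing has been once daily, and for those patients SAP Table 2 no longer contains a defined dosing-interval AUC. It also keeps CL/F while dropping AUC0-inf, from which single-dose CL/F is ordinarily derived, and %AUCextrap, which shows how much of that area is extrapolated.

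**Working it through.** **Step 1: which visit Day 22 is.** Protocol 6.1 defines a cycle as 21 days. Cycle 1 ends on Day 21, and Day 22 = 21 + 1 is C2D1. Day 22 is therefore outside the Cycle 1 sampling that SAP 8.9 itself describes.

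**Step 2: count the scheduled samples.**

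| Stage | Source | C1D15 | Day 22 |
|---|---|---|---|
| Escalation | Table 7-2 | nos. 14 to 24: 24 − 14 + 1 = 11 | no. 25: 1, pre-dose |
| Expansion, Phase II | Table 7-3 | nos. 7 to 12: 12 − 7 + 1 = 6 | 0 |

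The 11 include the 12 h draw, which is taken only if available, and the Day 16 pre-dose draw; without the 12 h draw there are 10. The 6 are pre-dose, 2, 4, 6, 8 and 24 h. Footnote 10 to Table 7-1 omits the 24 h draw and so gives 5; section 7.2.2.1 and Table 7-3 include it.

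**Step 3: compare with what the parameters need.** A peak and its time need several post-dose samples. An AUC needs at least two time points. Lambda-z needs at least 3 terminal points by the SAP's own rule, and half-life, CL/F and Vz/F depend on lambda-z or an AUC. One pre-dose sample gives a trough concentration and none of the listed parameters. At C1D15 all of them can at least be attempted.

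**Step 4: who AUC0-12 fits.** The escalation patients at the 18 January 2022 cutoff were:

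- BID: 3 (25 mg) + 3 (50 mg) + 4 (100 mg) = 10
- QD: 4 (400 mg) + 4 (600 mg) + 4 (800 mg) = 12

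The total is 22, and a further 4 patients were in the 600 mg QD expansion cohort. For QD patients AUC0-12 covers 12 of 24 hours.

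The share of the steady-state 24 h area that this captures can be illustrated from the protocol's half-life range of 8.42 to 10.9 h, assuming linear one-compartment kinetics with k = ln 2 / half-life.

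- Fast absorption: share = 1/(1 + e^(−12k)). For 8.42 h, e^(−12k) = 0.372 and the share is 0.729. For 10.9 h, e^(−12k) = 0.466 and the share is 0.682.
- Slowest first-order absorption consistent with that terminal half-life (ka = k), with x = 12k and q = e^(−24k): share = [1 − (1 + x)e^(−x)]/(1 − q) + 2xq(1 − e^(−x))/(1 − q)². This gives 0.533 for 8.42 h and 0.517 for 10.9 h.

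On these assumptions AUC0-12 would hold about 52% to 73% of a QD patient's steady-state daily exposure.

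**The case against.** The strongest reply is that this is a wrong label on a sound design. Sampling follows the protocol, whose full profiles fall on Day 1 and Day 15. Section 10.6.4 names C1D15 and refers to a separate PK analysis plan, which is not among the documents and may state the right day. A competent pharmacokineticist would notice. SAP section 7 also says that the programme has stopped and that many planned analyses may not be done. All of this limits the consequence, but none of it makes the SAP rule executable. SAP section 1 says that it details the analyses of protocol version 2.0, whose text is C1D15. The SAP's remark about further PK samples from some Phase II patients schedules no Day 22 profile.

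On the AUCs, AUC0-last implements the AUC0-t endpoint, which protocol Table 10-2 does not list, and AUC0-12 is the correct interval for BID patients. With a 24 h draw, AUC0-last approximates AUC0-24 in QD patients once the day is corrected. That much stands, and it is why both should be kept. It does not account for dropping three protocol parameters without declaring it.

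A reader might infer more than the documents support:

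- **That the PK endpoints are lost.** They are not. The endpoint lists name no day, the Day 1 set is unaffected by the wrong day, and the C1D15 samples are scheduled.
- **That a planned accumulation ratio is lost.** No such ratio is in either parameter table.
- **That the 3 to 4 fold accumulation in protocol 2.3 contradicts the stated half-life.** The protocol gives no metric, interval or schedule for that figure, and it pools BID and QD patients. One BID metric, daily steady-state AUC over first-dose AUC0-12, gives 2/(1 − e^(−12k)) = 3.19 to 3.75 with fast absorption, which would agree with it. No error is shown.

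**Conclusion.** SAP 8.9 is wrong as written. At its steady-state day there is 1 scheduled pre-dose sample per escalation patient and 0 per expansion or Phase II patient, against up to 11 and 6 at C1D15. None of the listed steady-state parameters can be produced from that. The conclusion rests only on the 21-day cycle and the two sampling tables.

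The undeclared change of AUC parameters is a second, smaller defect. It leaves QD patients, 12 of 22 in escalation at the cutoff, without a defined dosing-interval AUC. The 52% to 73% coverage figure is an illustration that depends on the protocol's half-life range and a simple model; the point that 12 h is not 24 h does not.

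The practical damage is modest. No data are lost, no patient is affected and no decision rule changes. It should still be corrected, because the SAP's rule cannot deliver the steady-state values of secondary endpoint parameters.

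**What to change.** - In SAP 8.9, replace Day 22 with C1D15 as the steady-state day.
- In SAP Table 2, restore AUC0-24, AUC0-inf and %AUCextrap, and keep AUC0-12 and AUC0-last. State that the dosing-interval AUC is AUC0-24 for QD patients and AUC0-12 for BID patients.
- List any PK difference from the protocol that remains in SAP 8.12.

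The cost is a corrected day label, three table rows, one sentence and an entry in 8.12, all using samples that the protocol already schedules. One limit should be acknowledged in the report: the 12 h draw is optional in Table 7-2 and absent from Table 7-3, so AUC0-12 in some BID patients will rest on extrapolation beyond 8 h and should be flagged.
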